## 1.0 Background

Forty percent of patients who develop acute respiratory distress syndrome (ARDS) will die during hospitalization. Among those who survive, 75% will develop long-term cognitive impairment (LTCI). LTCI is a growing public health problem and is defined as a new deficit or a worsening pre-existing deficit in cognition that remains persistent after an acute illness. Its reach extends beyond ARDS. Our research group observed that 34% of intensive care unit (ICU) survivors, regardless of ARDS status, develop cognitive impairment similar in severity to moderate traumatic brain injury and 24% develop even more severe impairments similar to mild Alzheimer's disease. A substantial proportion of ICU survivors will also develop impairments in executive function, which leads to increased disability, worsening quality of life, and reduced employment. Interventions that preserve long-term cognition and executive function after critical illness are lacking.

Early, high-dose oral Vitamin D repletion could potentially preserve long-term cognition in critically ill patients. Vitamin D is a pleiotropic secosteroid hormone that modulates systemic and central nervous system (CNS) inflammatory responses. Inflammation in response to an acute illness plays a prominent role in dementia pathogenesis. In addition to down-regulating systemic inflammation, Vitamin D also exerts its anti-inflammatory effects directly in the brain. Vitamin D receptors are located on microglial cells (CNS macrophages) which play a key role in neuroinflammation.

An abundance of recent observational data suggest Vitamin D deficiency is associated with poorer long-term cognition and increased risk of Alzheimer's dementia in community-dwelling adults. Based upon our preliminary studies, Vitamin D deficiency is also associated with accelerated cognitive decline in hospitalized, acutely ill patients. To our knowledge, no studies have evaluated if Vitamin D repletion improves these cognitive outcomes in the setting of an acute or critical illness.

## 2.0 Rationale and Specific Aims

A significant proportion of ICU survivors will acquire LTCI and executive dysfunction, especially in those who develop ARDS during hospitalization. These patients suffer from significant disability, a reduction in employment, and poorer quality of life. Because inflammation is likely to be an underpinning of LTCI pathophysiology, Vitamin D treatment can potentially improve long-term cognition by attenuating systemic and CNS inflammatory responses. Numerous observational cohort studies and our preliminary data have reported that Vitamin D deficiency is associated with LTCI and executive dysfunction. Randomized control trials designed to determine if Vitamin D repletion improves long-term cognitive outcomes are needed.

We propose this ancillary study to a parent double-blinded, placebo-controlled randomized control trial (RCT) evaluating how a single, high-dose (540,000 IU) oral Vitamin D3 treatment affects 90-day mortality in patients who are at high risk for ARDS and have Vitamin D deficiency (plasma 25-hydroxyvitamin D < 20 ng/ml). The parent RCT (Vitamin D to Improve Outcomes by Leveraging Early Treatment [VIOLET], NCT03096314) is part of the Clinical Trials Network for the Prevention and Early Treatment of Acute Lung Injury (PETAL) sponsored by the NHLBI. The VIOLET trial completed enrollment in July 2018 with 1,360 randomized patients. Our proposed ancillary study will provide additional funding to perform comprehensive neuropsychological (cognitive) evaluations, which were not part of the parent trial. These neuropsychological evaluations will be conducted 8 to 26 months after

randomization among a subset of 140 survivors enrolled in VIOLET. This ancillary study will be conducted in 7 (out of 42) sites. Our study, entitled VIOLET: Long-term **B**rain **O**utcomes in Vitamin **D** deficient patients (VIOLET-BUD), has the following hypothesis and specific aim:

**Aim:** Determine if early administration of a single high-dose (540,000 IU) oral vitamin D3 (cholecalciferol) treatment improves long-term global cognition and executive function as determined by comprehensive neuropsychological testing in 140 critically ill patients with Vitamin D deficiency at enrollment.

*Hypothesis: Critically ill patients with Vitamin D deficiency who are treated with a single high-dose of Vitamin D3 will have significantly better long-term global cognition and executive function than those treated with placebo.*

If Vitamin D is found to improve long-term (8 to 26 months after randomization) global cognition and executive function, then we will have discovered a novel therapy that would allow ICU survivors to keep their cognitive abilities and help them resume their lives as they did prior to the critical illness. Because oral Vitamin D is simple, inexpensive, and safe, this intervention could be feasibly implemented in ICUs worldwide.

### **3.0 Inclusion/Exclusion Criteria**

All patients enrolled in the VIOLET parent study will be considered for enrollment in VIOLET-BUD. VIOLET-BUD has the following exclusions:

- 1) Deaf or blind
- 2) Non-English speaking

Patients who are deaf or blind will be excluded, because the neuropsychological testing have auditory and visual components. Non-English speaking patients will be excluded because the neuropsychological raters can only perform the assessments in English only.

### **4.0 Enrollment/Randomization**

Because VIOLET-BUD is an ancillary study to the VIOLET parent study, randomization to the Vitamin D3 versus placebo group has been completed. The PETAL Clinical Coordinating Center performed computerized randomization using 1:1 allocation stratified by enrolling hospital. For VIOLET-BUD, the site research and clinical staff, patient and authorized surrogate will be blinded to treatment assignment.

VIOLET-BUD will enroll patients from 7 (out of 42) PETAL sites that participated in VIOLET. The local site will contact all patients who were enrolled in VIOLET to recruit patients for VIOLET-BUD. As part of the VIOLET parent study's informed consent document, participants agreed to be contacted for future studies. Although the patient contact will typically occur by phone, the initial method of contact may occur by e-mail, letter, or text depending on patient preferences or availability. To maximize the feasibility of the study, the long-term follow-up assessments conducted between 8 and 26 months) after randomization will be allowable. Patients enrolled in VIOLET will be contacted consecutively.

Once a VIOLET patient has been contacted, the local site study coordinator will use a phone or e-mail script (**Appendix A**). He/she will describe VIOLET-BUD's study protocol in lay terminology over the phone. It will be emphasized that the data collected will be for research purposes. The research staff will inform the patient that there is no obligation to

participate in the study. If the patient refuses to participate in VIOLET-BUD or died prior to the long-term follow-up, then this will be recorded. If the patient cannot follow-up because they reside in a skilled nursing facility or has significant mobility issues, lives too far from the local site, cannot obtain transportation to the local site, is incarcerated, or is too cognitive impaired to participate, then this will be recorded.

If the patient agrees to participate, then the local staff will review the informed consent document with the patient. Because patients may have LTCI significant enough to affect capacity, there is a possibility that the patient may not be capable of provide informed consent. In these cases, consent will be obtained from an authorized surrogate. The determination of whether or not a patient can provide informed consent will be determined by the study coordinator or investigators. They will be trained to determine who is not consentable through clinical judgment and direct patient interaction (**Appendix A**). Patients will be deemed capable of consenting if: 1) they are able to carry a normal adult conversation and 2) they are able to recall aspects of the consent (e.g. Can you tell me what the purpose and risks of the study are?"). The patient will be asked questions about the study to ensure they comprehend study procedures. If they unable to adequately answer these questions, then consent will be obtained from an authorized surrogate to also be contacted by phone.

If the patient or their authorized surrogate provides consent to participate in VIOLET-BUD, then the local site coordinator will setup an appointment for the patient to receive their outcome assessment at the local site. Patients will be contacted from 8 to 26 months after randomization in the parent study. Because the VIOLET parent study has completed enrollment, the wide enrollment window will facilitate recruitment and help achieve our sample size. After the appointment is setup, the local site study coordinator will send the patient or their authorized surrogate a copy of the informed consent document via their preferred method of contact. A letter (**Appendix B**) with the local site study coordinator's name and contact information, the appointment date, time, location, and a map with directions to the videophone neuropsychological testing area will also be enclosed or attached. On the day of the appointment, the patient or authorized surrogate will be provided an opportunity to ask additional questions. If they agree to participate in VIOLET-BUD, then they will sign the informed consent document. A copy of the informed consent document will be provided to the patient or their authorized surrogate. Afterwards, VIOLET-BUD's data collection, including the long-term outcomes, will be performed. Patients will be provided financial compensation once the long term follow-up visit has been completed.

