## **9.0 Statistical Considerations**

We will determine if single, high-dose enteral Vitamin D treatment improves long-term global cognition and executive function compared with placebo using multiple linear regression. One model will be constructed for long-term RBANS and another for long-term executive function. We will use multivariable linear regression over unadjusted analyses because it is hypothesized that there will be a 5% absolute risk reduction in death for those who receive enteral Vitamin D. This may imbalance potential confounders between the treatment and placebo groups. Additional imbalances may

occur because of random chance. Multivariable regression will minimize this bias and lead to moderate gains in power.

The models will be adjusted for the covariates listed in **Table 2**. Nonlinear predictor effects for continuous variables will be incorporated into the models. If necessary, non-normally distributed continuous variables will be transformed. To account for correlation within a center, we will use robust standard errors.

In the event of significant missing covariate data, *multiple imputation* will be considered.

Multiple imputation will also be performed if portions of the cognitive assessments are missing; patients with completely missing cognitive data will be excluded from the study. Because several of our covariates (e.g., premorbid cognition and intelligence) may be highly correlated, we will assess for collinearity using variance inflation factors and use only one of those variables if a high degree of collinearity is observed. The final models will be validated using bootstrap internal validation and cross validation approaches. After the initial analysis has been completed, we will also evaluate if there is any effect modification of age, dementia status (medical record), baseline severity of illness (SOFA), mechanical ventilation status, and ARDS status. We will also perform a sensitivity analysis where death within the follow-up window will be considered equivalent to the worst cognitive outcome. This will be performed to further determine the effect of death on our findings.

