Secondary analyses will be performed where we will determine how Vitamin D treatment affects the individual RBANS cognitive domains (e.g., immediate and delayed memory, attention, visuospatial construction, and language). We will also determine if treatment significantly improves long term functional status, employment as measured by the ICAP survey, nursing home placement, and death.

To estimate our sample size requirements, we used half a standard deviation (SD) of that particular test to define the minimum clinically important difference (MCID) threshold. Based upon the preliminary studies, the SD for the RBANS was 12. As a result, we considered a 6-point difference to be the MCID threshold for the RBANS. Based upon a two-sided alpha of 0.05 and 81% power, we will need outcome data in a total of 140 patients (~70 patients in each group) to detect a 6-point difference in RBANS between treatment groups. This sample size is feasible to obtain over 10 months. From September 2017 to July 2018, the six VIOLET-BUD sites enrolled 339 patients in VIOLET. Based upon the BRAIN-ICU study, we anticipate that 99% will not be deaf or blind, 62% will survive and 75% will follow-up at 8 to 26 months. We have the potential to enroll 155 patients making our required sample size of 140 patients very achievable. For our executive function composite score, the SD was 2.34 (**Section C6**), so the MCID threshold would be a 1.17 point difference. If we complete long-term executive function assessments on 140 patients as planned, we will have 81% power to detect this 1.17-point difference in the executive function composite score assuming a two-sided alpha of 0.05.

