## 10.0 Privacy/Confidentiality Issues

Covariates	df
Vitamin D vs placebo	1
Age	2
Severity of illness (SOFA)	2
Comorbidity (Charlson)	2
Pre-existing cognitive impairment	1
Time to long-term cognitive assessment	2
Premorbid intelligence	1
ARDS development	1

**Table 2.** Covariates for the multivariable linear regression models.

[name], MSc  
VIOLET-BUD

The patient's information, without identifiers, may be shared with other institutions or universities. [name], his co-investigators, and their staff will comply with any and all laws regarding the privacy of such information. There are no plans to pay the patient for the use or transfer of their de-identified information or specimens.

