### 3. Study Population

VIOLET-BUD enrolled subjects from November 2018 to October 2019 in 7 (out of 42) PETAL sites that participated in VIOLET. The local site contacted all patients who were enrolled in VIOLET to recruit patients for VIOLET-BUD. Originally, the objective was to conduct the follow-up assessments 12  $\pm$  4 months after randomization. Due to slower than anticipated enrollment, VIOLET-BUD expanded the follow-up window from 12 months to include all survivors. The median (interquartile range) time from randomization to follow-up was 443 (386.5, 481.5) days.

Patients were excluded from VIOLET-BUD if they were deaf, blind, or non-English speaking. Patients who were deaf or blind were excluded, because the neuropsychological testing has auditory and visual components. Non-English speaking patients were excluded because the neuropsychological raters can only perform the assessments in English.

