### 5.2. Adjusted analyses

$$\begin{array}{l} \text{Long-term RBANS} = \boxed{\text{Vitamin D versus Placebo}} + \text{Covariates} \\ \\ \text{Long-term executive function} = \boxed{\text{Vitamin D versus Placebo}} + \text{Covariates} \\ \text{composite score} \end{array}$$

**Figure 1.** Multivariable linear regression models

Covariates	Variable Type	df	Comment
Vitamin D vs placebo	Dichotomous	1	Primary independent variable
Age at enrollment	Continuous	2	
Pre-existing cognitive impairment	Dichotomous	1	Dementia or use of cholinesterase inhibitor prior to randomization
Severity of illness at enrollment	Continuous	2	Sequential Organ Failure Assessment (SOFA) score prior to randomization
Infection (Sepsis + Pneumonia) at enrollment	Dichotomous	1	Obtained by medical record review
Pre-illness intelligence at enrollment	Continuous	2	The Barona Index which is based on level of education, highest occupation, and region of residence 

**Table 2.** Covariates for the multivariable linear regression models in order of importance. The models will be able to accommodate 9 degrees of freedom.

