To determine if single, high-dose enteral Vitamin D treatment improves long-term global cognition and executive function compared with placebo, we will use multivariable linear regression or proportional odds logistic regression models based on the distribution of the continuous outcomes (**Figure 1**). Separate models will be constructed for long-term RBANS and executive function and adjusted for the baseline covariates listed in **Table 2**. Post-randomization covariates (e.g., interventions provided during hospitalization) will not be adjusted for because they may potentially be affected by the randomized intervention and be on the causal pathway. Prior to modeling, we will perform redundancy analyses to ensure that no covariates completely explain any of the others (resulting in multicollinearity) using an adjusted  $R^2$  cutoff of 0.7. If any covariates are highly correlated, only one of them based on clinical relevance will be kept in the model. If the multivariable models do not converge due to limited variability or low number of patients in specific levels of certain covariates, the number of covariates will be reduced based on the least rank in the order specified above. Restricted cubic splines for continuous variables will be incorporated into the models based on the distribution. To account for correlation among patients within a given site, we will adjust standard errors using Huber-White sandwich estimate. Partially missing long-term outcomes will be imputed using single imputation.

As exploratory heterogeneity of treatment effect analyses for primary outcomes, we will evaluate for effect modification by age, pre-existing cognitive impairment (e.g., dementia), baseline severity of illness (Sequential Organ Failure Assessment), infection (pneumonia or sepsis diagnosis), and pre-morbid intelligence (Barona). Because this is an exploratory analysis, we will consider an interaction term p-value less than 0.20 to suggest the potential presence of effect modification.

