## D5.2. Sample Size Calculations

In our original sample size calculations, we used half a standard deviation (SD) of that particular test to define the minimum clinically important difference (MCID) threshold. The SD for the RBANS in our population from previous studies was 12.4. Thus, we considered a 6-point difference to be the MCID threshold for the RBANS. Based upon a two-sided alpha of 0.05 and 80% power, we computed that we would need outcome data in a total of 140 patients with completed follow-up data (~70 patients in each group) to detect a 6-point difference in RBANS between treatment groups. However, VIOLET-BUD enrolled 95 patients; because the VIOLET parent trial stopped enrollment early, no additional patients could be recruited for this ancillary study. However, this sample size still provides us with more than 80% power to detect at least a

7.2-point difference. Some have considered an RBANS difference of 8 points to be the MCID threshold. For our executive function composite score, the SD in our previous population was 2.34. With 95 patients assessed, we will have greater than 80% power to detect a 1.4-point difference in the executive function composite score assuming a two-sided alpha of 0.05.

For our multiple linear regression models, we will have one degree of freedom available for every 10 to 15 patients with completed outcome measurements. Consequently, we will be able to accommodate 9 degrees of freedom for our multivariable models without overfitting.

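### Randomisation was stratified by enrolling hospital, but neither primary model contains hospital or site: a modest loss of precision and a possible, undemonstrated bias

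*Protocol*

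**What the plan says.** Protocol section 4.0 states that the coordinating centre "performed computerized randomization using 1:1 allocation stratified by enrolling hospital". It names no other stratification factor.

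Both documents deal with site, but only through the standard errors. Protocol section 9.0: "To account for correlation within a center, we will use robust standard errors". SAP section 5.2: "To account for correlation among patients within a given site, we will adjust standard errors using Huber-White sandwich estimate".

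The covariate lists contain no hospital or site term:
- Protocol Table 2 (printed under section 10.0): treatment, age, SOFA, Charlson, pre-existing cognitive impairment, time to assessment, premorbid intelligence and ARDS.
- SAP Table 2 and Figure 1: treatment, age, pre-existing cognitive impairment, SOFA, infection and the Barona Index. The table note adds: "The models will be able to accommodate 9 degrees of freedom".

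The SAP plans no site-adjusted sensitivity analysis. It reports recruitment "in 7 (out of 42) PETAL sites that participated in VIOLET", while the protocol's sample-size text refers to six: "the six VIOLET-BUD sites enrolled 339 patients in VIOLET". Neither document says whether enrolling hospital and site are the same unit.

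**The concern.** A factor used to stratify randomisation normally appears in the primary model. Here there is a further reason. The parent trial balanced the arms within each hospital, but the 95 assessed patients are those left after death, refusal, distance, transport problems, nursing-facility residence and severe impairment (protocol 4.0). Home visits are at each site's option (protocol 5.2). The arm ratio among assessed patients can therefore differ from site to site.

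If it does, and sites differ in mean score for reasons that the covariates do not capture, part of the site difference enters the treatment contrast. Possible sources are the local population, the proctor and the test setting. A sandwich variance changes the standard error and not the coefficient, so it cannot remove this.

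Precision is at stake in a study that reached 95 of 140 planned patients. SAP section 5 itself justifies adjustment by power and precision. If retention also depended on arm differently across sites, some bias would be possible.

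**Working it through.** **1. The plan's own figures.** SAP Table 2 sums to 1 + 2 + 1 + 2 + 1 + 2 = 9 df. The SAP's rule is that "we will have one degree of freedom available for every 10 to 15 patients with completed outcome measurements". At 10 per df, 95/10 = 9.5, so 9 df fit (95/9 = 10.6 patients per df). With SD 12.4 and 47.5 patients per arm (equal arms assumed), the standard error is 12.4 × √(2/47.5) = 2.54. The difference detectable with 80% power is (1.960 + 0.842) × 2.54 = 7.13 points. Power for 7.2 points is 80.8% (normal approximation). Both agree with the SAP's 7.2 points.

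**2. Site error left in the estimate.** Let the site means vary with SD σ_s = 12.4 × √ICC. The error in the treatment contrast is Σ_s u_s (p1_s − p0_s), where u_s is the site effect and p1_s, p0_s are the shares of each arm that come from site s. It is zero when every site has the same arm ratio, even an unequal one. What matters is that the ratio differs between sites.

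If retention is unrelated to arm and the arms are about equal overall, the SD of this error is

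σ_s × √[ (4/(N − 1)) × (1 − Σ(n_s/N)²) ].

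Assumed site sizes: 30, 20, 15, 12, 8, 6, 4 (total 95). Then Σn_s² = 1,785, 1 − 1,785/9,025 = 0.802, and √(4/94 × 0.802) = 0.185.

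| Assumed ICC | σ_s | SD of site error (RBANS points) | Share of variance 2.54² |
|---|---|---|---|
| 0.05 | 2.77 | 0.51 | 4% |
| 0.10 | 3.92 | 0.72 | 8% |

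Simulation agrees: 0.54 and 0.74 with near-equal sites; 0.51 and 0.72 with sizes 35, 20, 12, 10, 8, 6, 4. The 95th percentile of the absolute error is about 1.0 to 1.1 points at ICC 0.05 and 1.5 at 0.10. None of this allows for the SAP covariates, which would reduce it.

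**3. Effect of a random site intercept.** Simulated change in the variance of the treatment estimate (sizes 30 to 4 as above, arms random within site, no other covariates):
- ICC 0: about +0.7%
- ICC 0.05: about −2% (separate runs gave −1% to −2%)
- ICC 0.10: −4% to −6%

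At ICC 0 the detectable difference moves from 7.13 to 7.13 × √1.007 = 7.15 points.

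**4. Effect of fixed site effects.** Seven sites add 6 df: 9 + 6 = 15, and 95/15 = 6.3 patients per df, outside the SAP's rule. With six sites the figures are 14 df and 6.8. If sites do not differ, the variance rises by about 7%. The detectable difference goes to 7.13 × √1.07 = 7.37 points, and power at 7.2 points falls from 80.8% to 78.1%.

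**The case against.** The strongest reply is that no bias has been shown, and this stands. A reader might infer that the primary estimate is confounded by site. The documents do not support that:
- Site staff, patients and surrogates are blinded (protocol 4.0), so distance, transport and home-visit choices offer no evident route to arm-specific retention.
- Testing is done by one central group of neuropsychologists by videophone, blinded to arm (protocol 5.2). The local proctor mainly assists.
- The covariates absorb some case mix, and the Barona Index includes region of residence. Time to assessment has a sensitivity analysis in the SAP.
- If retention is unrelated to arm, the site error is chance error, not systematic bias.

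A reader might also build a striking example. Suppose a 20-patient site scores 10 points below the rest and retains 13 placebo and 7 vitamin D patients. The shift depends on the other 75 patients:
- 40 placebo and 35 vitamin D: 10 × (13/53 − 7/42) = 0.8 points
- 35 and 40: 10 × (13/48 − 7/47) = 1.2 points
- 33 and 42 (46 and 49 overall): 10 × (13/46 − 7/49) = 1.4 points

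The largest figure needs an opposite imbalance at the other sites. The 10-point gap is itself an assumption, 0.8 SD before adjustment. It should not be read as an expected shift.

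A third objection is that a random intercept does not fully restore the within-hospital comparison. This also stands. It shrinks the site effects, and with seven sites the estimated site variance was zero in about 26% of simulated trials at ICC 0.05, which leaves the estimate unchanged.

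The objection that a site term breaks the 9-df budget applies to fixed effects only.

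**Conclusion.** The omission is real: the only stated stratification factor is in neither primary mean model, and robust standard errors do not make up for that in the point estimate. Site is not ignored, since both documents allow for within-site correlation.

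The consequence is modest. The added error has an SD of about 0.5 RBANS points at ICC 0.05 and 0.7 at 0.10, beside a standard error near 2.5 and a 6-point minimum important difference. These sizes rest on an assumed ICC, assumed site sizes, random retention and no other covariates. The same argument applies to the executive function composite, on its own scale.

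Bias remains possible but cannot be judged without the counts of assessed patients by site and arm. The change is worth making because its cost is very small and it follows the design, not because the planned result is shown to be wrong.

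**What to change.** - Add the randomisation stratum (enrolling hospital, or site if hospital counts are too small) as a random intercept in both primary models. This adds one variance parameter and uses none of the 9 fixed-effect df. Say that the adjustment is partial, because site effects are shrunken.
- Keep the model without site as a sensitivity analysis. Use fixed site effects as a sensitivity analysis only, given 15 df on 95 patients.
- If the proportional odds branch is used, include the same intercept and state that the odds ratio is then conditional on site.
- State whether the sandwich errors are kept alongside the random intercept, and on which unit they are clustered.
- Tabulate assessed patients by site and arm, say whether hospital and site are the same unit, and reconcile six with seven sites.

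Cost: a short SAP addition, using data already held. Statistically, it is about 0.7% more variance if sites do not differ.

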To determine how time to neuropsychological assessment impacted our findings, we will also conduct a sensitivity analysis; we will re-run the multivariable regression models adjusting for time to neuropsychological assessment. Patients were included in VIOLET (and VIOLET-BUD) if their plasma Vitamin D concentrations were < 20 mg/dL as determined by local immunoassay (clinical laboratory or point-of-care) testing. The VIOLET parent trial also confirmed baseline (pre-randomization) Vitamin D deficiency using liquid chromatography-mass spectrometry (LC-MS), the gold standard for Vitamin D measurement, conducted at the University of Washington on batched samples after 90-day follow-up was completed. VIOLET-BUD's primary analyses will use immunoassay Vitamin D measurements. We will re-run the multivariable regression models and adjust for baseline Vitamin D levels as measured by LC-MS as a sensitivity analysis. Because the VIOLET parent study did not observe a significant difference in 90-day mortality between the Vitamin D and placebo groups, analyses accounting for differential mortality will not be performed.

Other secondary analyses will include associations between Vitamin D treatment and individual RBANS cognitive domains (e.g., immediate and delayed memory, attention, visuospatial construction, and language) and executive function subscales (DKEFS Proverbs, Trail Making-Number/Letter Switching, and Verbal Fluency Category Switching). We will also determine if treatment is associated with functional status (Katz and Lawton).

Level of statistical significance will be set at 5%. All tests will be two-sided and 95% confidence intervals will be reported along with all effect estimates. Presentation of results will emphasize clinical significance, effect sizes, and confidence intervals, over statistical significance. Regarding the analyses of all *a priori*-defined secondary outcomes described herein, no adjustments will be made for multiple comparisons in keeping with recommendations on this topic and standard practice when analyzing multiple, prospectively defined outcomes in a clinical trial.

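### Survivors recorded as too impaired to be tested have no cognitive score and enter no planned analysis, so inclusion depends on the primary outcome in an extreme low tail of unknown size

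*Protocol*

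**What the plan says.** Protocol 3.0 opens the ancillary study to the whole parent cohort ("All patients enrolled in the VIOLET parent study will be considered for enrollment in VIOLET-BUD") and lists two exclusions: deaf or blind, and non-English speaking. Cognitive impairment is not among them. Protocol 4.0 foresees severe impairment ("Because patients may have LTCI significant enough to affect capacity, there is a possibility that the patient may not be capable of provide informed consent") and provides for it: "In these cases, consent will be obtained from an authorized surrogate".

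The same section lists reasons why a contacted survivor may be unable to attend: skilled nursing residence or mobility, distance, transport, and finally that the patient "is incarcerated, or is too cognitive impaired to participate, then this will be recorded". Recording is the only action. No criterion is given for the last reason; the test described in 4.0 concerns capacity to consent.

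Protocol 9.0 multiply imputes partly missing cognitive assessments, but "patients with completely missing cognitive data will be excluded from the study". SAP 5.2 says "Partially missing long-term outcomes will be imputed using single imputation" and is silent on wholly missing outcomes.

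Two protocol analyses go beyond tested patients, and both concern death: a sensitivity analysis in 9.0 in which "death within the follow-up window will be considered equivalent to the worst cognitive outcome", and the survivor average causal effect in 5.2. The SAP withdraws this line of work: "analyses accounting for differential mortality will not be performed".

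**The concern.** The co-primary outcomes are global cognition and executive function. A survivor logged as too impaired to be tested is lost because of the very quantity being measured, and that quantity arises after randomisation. Refusal or distance need not track the endpoint; this reason does by definition. Adjustment for baseline covariates does not repair it, because selection acts on the unobserved outcome given those covariates.

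The plan's own reasoning points the same way. The protocol treats death as informative about cognition, and a living patient who cannot be tested is a more direct instance of poor cognition. SAP 5.2 declines to adjust for post-randomisation variables because treatment may affect them; selecting patients on post-randomisation cognition raises the same difficulty. At stake is the size of the estimated effect, and some power, in a study that already fell from 140 planned to 95 enrolled.

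**Working it through.** **1. The plan's own figure.** SAP D5.2 gives SD 12.4, a 6-point difference, two-sided alpha 0.05 and 80% power. Then n per arm = 2(1.96 + 0.842)² × 12.4² / 6² = 67.05, so 68 per arm and 136 in total, against the stated 140. With 70 per arm, power is 81.7% (normal approximation), which agrees with the protocol's 81%. The protocol prints SD 12, which would give 84.1%; 12.4 is therefore used below. With 95 patients (47.5 per arm), the standard error of the difference is 12.4 × √(2/47.5) = 2.54 points, and power for 6 points is about 65%.

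**2. How many are lost.** The documents do not say. Protocol 9.0 plans on 339 × 0.99 × 0.62 = 208 eligible survivors, of whom 25%, about 52, are not assessed for any reason. No breakdown by reason or by arm is given.

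**3. Effect on the difference.** Assumptions not in the documents: RBANS means of 80 (placebo) and 86 (vitamin D), and a single cut-off c below which nobody can be tested. For each arm, a = (c − μ)/12.4, the untestable share is Φ(a), and the mean of those tested is μ + 12.4 × φ(a)/(1 − Φ(a)).

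| Cut-off | Untestable, placebo | Untestable, vitamin D | Tested mean, placebo | Tested mean, vitamin D | Difference | Shrinkage |
|---|---|---|---|---|---|---|
| 55 | 2.2% | 0.6% | 80.66 | 86.22 | 5.56 | 7% |
| 60 | 5.3% | 1.8% | 81.42 | 86.56 | 5.14 | 14% |
| 65 | 11.3% | 4.5% | 82.68 | 87.23 | 4.55 | 24% |

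**4. Direction.** Writing λ = φ(a)/(1 − Φ(a)), the tested mean changes with μ at rate 1 − λ(λ − a), which lies between 0 and 1 for a normal outcome. So a common threshold shrinks any true difference, benefit or harm. If both arms have the same mean, the tested means are equal and the expected bias is zero.

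**5. Effect on power.** This is a simulation with 5,000 runs per row, SD 12.4, a true difference of 6 and about 95 tested patients. Complete cases are compared by t-test. The alternative is a Mann-Whitney test that keeps untestable survivors at a shared worst rank. Neither is covariate-adjusted.

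| Untestable, placebo / vitamin D | Complete-case difference | Complete-case power | Worst-rank power |
|---|---|---|---|
| 0 / 0 | 6.0 | 66% | 64% |
| 2% / 0.6% | 5.6 | 61% | 63% |
| 5% / 1.7% | 5.2 | 58% | 63% |
| 10% / 3.9% | 4.6 | 53% | 64% |
| 15% / 6.4% | 4.2 | 50% | 67% |

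**The case against.** A reader might infer that the protocol screens patients out on cognition, or that the worst living outcomes as a group are removed. The documents do not support either. The sentence in 4.0 logs why a contacted patient cannot attend; it is not an eligibility criterion and does not conflict with 3.0. Surrogate consent covers lack of capacity, Protocol 5.2 allows a visit at home for those who cannot travel, and Protocol 6.0 lets a tired or distressed patient rest, reschedule or skip a task, after which partial data are imputed. Only survivors who yield no score at all are lost.

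A reader might also infer that the omission could readily produce a false benefit. Site staff are blinded and no arm-specific threshold is suggested. Under a common threshold the expected error is toward no difference, and a spurious effect needs a chance imbalance in the few patients lost.

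Two further objections stand in part. The size is hypothetical, since neither document gives RBANS means by arm, a testability cut-off or counts. And this reason is one of several: a severely impaired nursing-home resident may be logged under residence and so be missed by a remedy keyed to one label.

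What survives is the gap itself. For those who remain untestable after every accommodation, neither document plans any analysis.

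**Conclusion.** The concern holds in limited form. Survivors too impaired to be tested are excluded under Protocol 9.0 and reached by no primary or sensitivity analysis in either document, so inclusion depends on the primary outcome after randomisation. The number affected is unknown and is probably confined to an extreme tail. If 2.2% to 11.3% of placebo survivors were untestable under the assumed means and a common cut-off, a true 6-point difference would appear as about 5.6 to 4.6 points. That loss of 0.4 to 1.4 points compares with a standard error of about 2.5 at 95 patients. With no treatment effect the expected bias is zero. The documents do not show that the result is biased; they show that the plan has no means of finding out. Confidence is moderate.

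**What to change.** In SAP 5.2:

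1. Report the recorded reasons for non-assessment by treatment arm, for all parent-trial patients at the participating sites, beside the primary result.
2. For each primary outcome, add one sensitivity analysis that includes survivors recorded as too impaired to take part, at a shared rank below the lowest observed score. Fit it with the proportional odds model that SAP 5.2 already names. Adjust for parent-trial covariates available for everyone, such as age and SOFA. Add pre-existing cognitive impairment where the record review covers these patients; Protocol 5.2 extends that review to those who died or refused and does not mention this group. Do not require the Barona Index, because education, occupation and region are collected by the ancillary study from the patient or informant (Protocol Table 1 and 6.0) and may be missing here.

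The cost is a short SAP addition, one table and one model per outcome, using reasons the sites were already told to record and allocation known from the parent trial. There are three downsides: being too impaired is a site judgement with no stated criterion, some such patients may be logged under another reason such as skilled nursing residence, and the covariate set is smaller than in SAP Table 2. For these reasons it should remain a sensitivity analysis. If the counts prove to be zero or negligible in both arms, the table alone largely settles the matter.
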